3.0 Subject Selection

3.1 Number of Subjects and Subject Selection

This feasibility study aims to randomise 102 men within a period of twelve months. The study population is male patients over 16 years of age, who have been diagnosed with prostate cancer, have an estimated life expectancy of more than three years, and who have opted for Active Surveillance as their preferred prostate cancer therapy.

Participants must fulfil the inclusion and exclusion criteria. All patients who meet the eligibility criteria and are randomised will be included in the intention to treat (ITT) analysis.

17 men will be randomised into each of the six study arms in a 3 x 2 factorial design with a 1:1:1:1:1 ratio. In order to maintain treatment blinding, placebo aspirin will be size matched with the active treatment, and given as either a small (100mg) size or standard (300mg) size.

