Patients may withdraw from the trial at any time at their own request or they may be withdrawn at any time at the discretion of the investigator if it is considered to be in the best interest of the patient. Patients can withdraw without giving a reason, but if a reason is given this should be documented in the eCRF and medical notes. It is possible for a patient to withdraw from treatment but continue to be followed up via eCRF, in clinic or by telephone. A 'Withdrawal from Treatment' eCRF will be completed. If patients do not wish to continue in this way, an 'End of Study' eCRF will be completed and they will not have any further visits.

The main analyses will be by intention to treat, therefore, data and samples collected up to the time of withdrawal of consent will be included in the study analyses, as stated in the consent form. Such data or samples will be included in the analysis, unless explicitly forbidden, again, in writing by the participant.

Patients may be withdrawn from trial medication, and/or the study in the event of:

- Unacceptable toxicity/intolerable side effects
- Inter-current illness
- Patient withdrawing consent
- Patient unable to comply with the study schedule
- Interruption of study drug intake for greater than 60 days
- Patient chooses to come off Active Surveillance and undergo active therapy
- Rise in serum calcium above upper limit of normal or 2.65mmol/l
- Identification of higher risk disease unsuitable for surveillance following 'For Cause' repeat prostate biopsy precipitated by an increasing PSA
- Development of new dyspeptic symptoms, or any sign of gastro-intestinal bleeding (haematemesis, melaena, decreased haemoglobin)
- Any episode of haemorrhage or development of a bleeding disorder
- Development of a condition not compatible with the study, or the addition of a new incompatible medication e.g. NSAID, or other product as in section 4.10
- Disease progression

Data concerning toxicity will be collected using the diary cards issued to all participants, which will allow symptoms to be classified as mild, moderate or severe. Data will also be collected on the Case Report Forms regarding gastro-intestinal bleeding and hypercalcaemia. Blood calcium levels will be monitored six monthly and any emergency hospital admissions reported, in which hypercalcaemia is identified, will be documented and followed up by the research team.

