Patients who interrupt study drug intake for a cumulative total of greater than 60 days, in a 3 month period between follow-up appointments, will be considered as non-compliant and will be discontinued from the study. An 'End of Study, eCRF will be completed, and no further follow-up appointments conducted. These patients will be included in the intention to treat and safety analyses. They will be included in the efficacy assessment only if they have received at least three 90 day cycles of treatment.

Patients will be considered to be lost to follow-up if there has been as no contact for ≥6 months from the last scheduled clinic visit. These patients will be included in the intention to treat and safety analyses. They will be included in the efficacy assessment only if they have received at least three 90 day cycles of treatment.

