Administration of IMP will be discontinued in the following circumstances:

- Development of hypercalcaemia confirmed by blood sample
- Development of new dyspepsia symptoms or gastro-intestinal bleeding
- Development of a condition which requires treatment with a prohibited concomitant therapy
- Development of a condition which, in the judgement of the investigator, adversely affects the participant's safety, compliance or ability to complete evaluations
- If the investigator concludes that this course of action is in the participant's best interests

Should a patient become concerned that a symptom is potentially related to a study medication, it would be preferable to consider a dose interruption e.g. an alternate daily dose, or offer a 'treatment holiday', rather than stop treatment completely. Dose interruptions can be up to 30 days in the case of suspected toxicity. Longer 'treatment holidays' must be discussed with the PROVENT CCO. However, patients who interrupt study drug intake for a cumulative total of greater than 60 days, in a 3 month period between follow-up appointments, will be considered as non-compliant and will be discontinued from the study. An 'End of Study, eCRF will be completed

'Treatment holidays' can also be used in other special circumstances, at the discretion of the PI, but any dose interruptions of greater than two weeks, for reasons other than toxicity must be discussed with the PROVENT CCO. All variations in dose regime/daily dose, must be documented on the relevant eCRF, & in the patient diary.

Full treatment may be restarted after an appropriate interval, (no longer than 60 days), if symptoms have resolved, or a decision may then be made about withdrawal, if symptoms persist. Any variation in dose regime should always be documented on the relevant Case Report Form and in the patient diary.

Participants who discontinue the study drugs for any reason will not be considered to have left the study, and will be followed up for primary and secondary outcome measures. These patients will be included in the intention to treat and safety analyses.

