5.12 Data Collection and Follow Up for Withdrawn Subjects

Data collected up to the time of withdrawal of consent will be included in the study analyses, as stated in the consent form, unless participants specifically withdraw permission to do so in writing. With the exception of such patients, withdrawn subjects will remain under three monthly follow-up in clinic for the duration of the trial, as the main analyses will be by intention to treat.

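### The three-cycle condition for entering the efficacy assessment is not marked as supplementary, so it can take the secondary drug comparisons off the randomised groups

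*Protocol*

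**What the plan says.** Section 3.1 defines the intention-to-treat set: "All patients who meet the eligibility criteria and are randomised will be included in the intention to treat (ITT) analysis". Section 3.4, under early withdrawal, gives the principle: "The main analyses will be by intention to treat". It draws the consequence that data collected before consent is withdrawn are analysed. Section 5.12 repeats the principle.

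Section 3.4 then treats two groups separately. The first is "Patients who interrupt study drug intake for a cumulative total of greater than 60 days, in a 3 month period between follow-up appointments"; these men are called non-compliant and discontinued. The second is men without contact for six months or more after their last scheduled visit. For each group it says "These patients will be included in the intention to treat and safety analyses", and in the next sentence "They will be included in the efficacy assessment only if they have received at least three 90 day cycles of treatment".

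The protocol does not say what the efficacy assessment is. Section 8.1 (recruitment) and section 8.2 (MRI, biochemical and histological progression, and markers) are both headed as efficacy analyses. Section 8.2 reports MRI and biochemical progression as proportions of the study cohort. Section 8.5 plans a stratified Wilcoxon test of each drug against its placebo and a mixed model on log(1+PSA), without naming the men who enter either.

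Follow-up is stated in three ways. For non-compliant men, section 3.4 has "no further follow-up appointments conducted". Section 4.11 says "Participants who discontinue the study drugs for any reason will not be considered to have left the study" and that these men are followed for primary and secondary outcomes. Section 5.12 says "withdrawn subjects will remain under three monthly follow-up in clinic for the duration of the trial", except for those who withdraw permission in writing.

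**The concern.** Treatment received is known only after randomisation and may depend on the drug and on the patient's prognosis. If entry to a comparison depends on it, the groups compared are no longer those that were randomised. Here the condition is attached to the word efficacy, which is also the heading over the outcomes compared between drug and placebo, and nothing marks it as secondary to the intention-to-treat analysis. An analyst who follows section 3.4 literally would drop PSA and assay values already collected from these men.

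The stake is limited but real. Section 1.5 says the numbers for a definitive protocol will be identified through the disease progression rate. A rate taken from men selected on exposure would be a poor input. The groups are also small, so each exclusion counts.

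**Working it through.** **1. The plan's own figure.** The one reproducible design figure is the 89% power in section 8.4: n = 300 approached, 33.3% against 25%, two-sided 0.05.
- Standard error under 25%: √(0.25 × 0.75 / 300) = 0.0250, so the critical proportion is 0.25 + 1.96 × 0.0250 = 0.299.
- Standard error under 1/3: √(0.3333 × 0.6667 / 300) = 0.0272.
- Power = Φ((0.3333 − 0.299) / 0.0272) = Φ(1.26) ≈ 0.896. The exact binomial test (reject at 91 or more) gives 0.878.

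The 89% reproduces. It concerns recruitment before any drug is taken, so the three-cycle condition cannot affect it.

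**2. Who the condition reaches.** It covers only men with more than 60 days' interruption in a three-month period and men lost to follow-up. Section 4.11 deals with interruptions for suspected toxicity and applies the same 60-day limit to them, so drug-related stopping can reach the condition by that route.

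**3. Group sizes.** Six arms of 17 give 34 men on each aspirin level and 51 on each side of the vitamin D3 comparison. One excluded man is 1/34 = 2.9% of an aspirin group.

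**4. What exclusion could do.** Let true progression be 30% in every arm (section 3.4 gives up to 30%) with no drug effect. If a share e is excluded and those men progress at rate q, the retained men progress at (0.30 − e·q) / (1 − e). The shares e and rates q below are assumptions; the protocol gives neither. Placebo exclusion is set at 5%.

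| Excluded on active | q = 10% | q = 30% | q = 50% |
|---|---|---|---|
| 5% | 0 | 0 | 0 |
| 10% | +1.2 points | 0 | −1.2 points |
| 15% | +2.5 points | 0 | −2.5 points |
| 20% | +4.0 points | 0 | −4.0 points |

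Entries are active minus placebo. Example at 20% and q = 50%: (0.30 − 0.10) / 0.80 = 25.0% on active, (0.30 − 0.025) / 0.95 = 28.9% on placebo, a difference of −4.0 points after rounding. The sign depends on the excluded men's prognosis. The bias vanishes if they progress like the others, or if exclusion is balanced with the same prognosis in both arms.

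For scale, the standard error of a 34-against-34 difference at 30% is √(2 × 0.3 × 0.7 / 34) = 11.1 points.

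**5. What is lost through follow-up.** Section 5.4 places the repeat biopsy at weeks 48 to 56, that is days 336 to 392. A man discontinued with fewer than 270 days of drug will usually have been closed out before then. If section 3.4 is followed, he has no trial MRI, biopsy or PSA at 12 months, and his place in the intention-to-treat analysis of progression is nominal. If sections 4.11 and 5.12 are followed, he has those outcomes, and the three-cycle condition would discard them.

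**The case against.** The strongest reply is that section 3.4 retains these men in the intention-to-treat analysis in the sentence just before the condition. Read with the statement that the main analyses are by intention to treat, the efficacy assessment may be a third, exposure-based set beside the intention-to-treat and safety sets. Section 8.2's cohort denominator fits that reading, and section 10 refers to a statistical analysis plan, where sets are commonly defined. This stands to the extent that a reader might infer a flat contradiction of intention to treat, and the text does not support that. What remains is that the protocol itself fixes an entry rule for efficacy, places the compared outcomes under an efficacy heading, and does not say which set governs.

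A reader might also infer that men stopped for dyspepsia or bleeding on aspirin are removed, giving aspirin a false benefit. The documents do not support this. Section 3.4 lists those events separately from the 60-day interruption, no passage attaches the three-cycle condition to them, and the direction of any bias is open.

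It may be said that the condition is unworkable because no 90-day cycles are defined. This is weak: visits and diary cards are three-monthly, so the term has a natural meaning. Whether it counts days elapsed or days taken is still not stated.

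Finally, the stakes are modest. The decision to proceed rests on recruitment and adverse effects (sections 2.3 and 8.1), and section 8.4 already gives 800 men for the definitive trial. That bears on severity, not on whether the text needs correcting.

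**Conclusion.** The point holds as an ambiguity with a possible bias. As written, section 3.4 allows a post-randomisation exclusion on about 270 days of treatment to be applied to the secondary drug-versus-placebo comparisons, although sections 3.4 and 5.12 declare intention to treat. The exclusion could bias those comparisons and the progression rate carried into planning.

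No size or direction follows from the protocol. The 1 to 4 points in either direction rest wholly on assumed exclusion shares of 10 to 20% against 5%, and on excluded men progressing at 10% or 50% rather than 30%. These shifts are well inside the sampling error of groups this small. The primary endpoint, its power and the target of 102 are untouched. The correction is worthwhile and cheap, but it does not put the trial's main purpose at risk. The conflict over follow-up is part of the same problem, because it decides whether the intention-to-treat analysis has outcomes to use.

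**What to change.** 1. State in sections 3.4 and 8.5 that the secondary efficacy comparisons use all randomised men as allocated, with every outcome obtained.
2. In both paragraphs of section 3.4, remove the three-cycle condition from those comparisons. If an exposure-based set is wanted, keep it as a labelled supplementary on-treatment analysis, with exposure defined in days of drug taken.
3. Reconcile section 3.4, which ends follow-up of non-compliant men, with sections 4.11 and 5.12, which continue it. Section 4.11 should also be made consistent within itself, since it has some men withdraw from the study and elsewhere says men who stop drug have not left it. Removing the condition alone would recover little 12-month outcome data.

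Items 1 and 2 are wording changes, to be mirrored in the statistical analysis plan and settled before unblinding; they need no new data. Item 3 has a cost if it leads to more outcome collection after discontinuation. Sections 5.4 and 5.8 describe the 12-month MRI and biopsy as routine care, so the added burden should be mainly data capture within each man's consent. Sample size and power do not change.

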4.0 Investigational Medicinal Product

Further information can be found in the PROVENT IMP/Pharmacy Manual & IMP Management Plan.

4.1 IMP details

Aspirin, Vitamin D3 and placebos are considered IMPs in this trial.

Vitamin D3 active product

Trade name: Vigantol® Oil

Composition: 0.5mg Vitamin D3/ml in Miglyol®812 vehicle oil

(40 drops/1ml = 20,000 IU/0.5mg cholecalciferol)

Presentation: Glass bottle with dropper containing 10mls Vigantol® Oil Dosage regimen: 8 drops or 4,000 IU (0.1mg) per day over 18 months

Route of administration: Oral

Vitamin D₃ placebo

Trade name: Miglyol®812 Oil

Composition: A pharmacopoeia-listed mixture of palm oil and coconut oil

containing medium chain triglycerides that is used as the excipient for Vitamin D3 in Vigantol® Oil; it is thus identical to Vigantol® Oil in every

respect (except for the absence of Vitamin D3)

Presentation: Glass bottle with dropper containing 10mls Miglyol® 812 Oil

Dosage regimen: 8 drops placebo oil per day over 18 months

Route of administration: Oral

Aspirin standard dose active product

Composition: acetylsalicylic acid

Presentation: HDPE plastic bottles containing white enteric coated tablets

Dosage regimen: 1 x 300mg tablet daily over 18 months

Route of administration: Oral

Aspirin low dose active product

Composition: acetylsalicylic acid

Presentation: HDPE plastic bottles containing white enteric coated tablets

Dosage regimen: 1 x 100mg tablet daily over 18 months

Route of administration: Oral

Aspirin Placebo in two sizes

Composition No active ingredient

Presentation: HDPE plastic bottles containing white enteric coated tablets matched

to either 300mg or 100mg size

Dosage regimen: 1 x tablet daily over 18 months

Route of administration: Oral

NB: No IMPD is provided for the Aspirin placebo even though it differs in composition from the active IMP because, as noted in CT-1, this placebo has been submitted to the Regulatory Authority in the UK,

and the manufacturer concerned has provided a Letter of Authorisation for access to the sIMPD for this placebo.

In the case of

4.2 Formulation of IMP

Vitamin D₃ Oily solution containing 0.5mg Vitamin D₃ per ml in Miglyol®812

vehicle oil

Vitamin D₃ placebo Miglyol®812 oil identical to Vigantol® Oil without the addition of

VitaminD₃

Aspirin standard dose White enteric coated tablets containing 300mg aspirin

Aspirin low dose White enteric coated tablets containing 100mg aspirin

Aspirin placebo White enteric coated tablets identical in appearance but not

composition to aspirin 100mg and aspirin 300mg. In addition they are

without the active ingredient

4.3 IMP supply

The Vitamin D_3 and matched placebo, and aspirin and matched placebos will be manufactured and supplied according to principles of GMP, and supplied specifically for the PROVENT study. Each pack will carry a unique medication code.

Manufacturer/supplier of Vitamin D3 Merck Serono GmbH

and matched Vitamin D3 placebo: [name]

[name]

Germany

Merck Sorono will obtain vehicle oil

for Vitamin D3 and placebo from:

Caesar & Loretz GmbH

[name]

[name]

Germany

Manufacturer/supplier of aspirin and

matched aspirin placebos:

Bayer HealthCare Pharmaceuticals

Bayer Pharma AG [name]

[name]

4.4 Prescription of IMP

The Trial Delegation Log will specify the names of all study staff authorised to prescribe the IMP for this study. Study specific prescription and dispensing forms that have been pre-agreed with the pharmacy will be used.

Pharmacies will be provided with a copy of the current Delegation Log to ensure that they are aware of the assigned prescribing healthcare professionals for the study at that site.

4.5 Preparation and Administration of IMP

Six months' supply of IMP will be issued at randomisation, and then subsequently every six months during a follow-up visit. Each six months' supply will consist of:

5 bottles each containing either 10ml Vigantol® Oil (oily solution of Vitamin D3, concentration 0.5mg/ml) or 10ml Miglyol®812 Oil (placebo)

PLUS

4 HDPE plastic bottles, each containing 52 gastro resistant tablets of either 300mg aspirin or 100mg aspirin or placebo aspirin.

The quantity of IMP dispensed on each occasion will be sufficient to allow for two late running or missed appointments. The study medication will be taken for 18 months, unless prostate cancer progression is found at the 12 month, 'for cause' biopsy appointments, in which case medication will be discontinued.

Aspirin

The once daily dose of aspirin or placebo aspirin will be given orally, and should be swallowed whole with water. It should be taken with food at the same time each day. A missed dose of study drug may be taken later, providing there are at least 6 hours before the next scheduled dose. Patients will be given a diary card as an aide memoire, and if a dose is missed completely, it should be recorded as 'not taken' in the patient diary.

Compliance will be assessed six monthly. Patients will be requested to bring their remaining study medication to their six, twelve and 18 month visits for reconciliation by the pharmacy. The number of tablets taken will be calculated by subtracting the number of tablets returned from the number of tablets dispensed, and the diary card will provide supporting information if necessary.

Participants will be advised that aspirin or placebo aspirin tablets should be stopped 7 days prior to any surgical procedure wherever possible (see section 4.11)

Vitamin D3

The daily dose of Vitamin D3 or placebo will also be taken orally. It will be presented as 8 drops of oily solution that can be swallowed from a teaspoon or soaked into bread to aid palatability. A missed dose of Vitamin D3/placebo may be taken later the same day, or with the next dose, however, if a dose is missed completely, it should be recorded as 'not taken' in the patient diary.

Patients who vomit after taking the study medication will be advised not to take any further study medication that day, but to document the event on their diary card. Subsequently, if they continue to vomit after taking their medication they should stop the medication and contact their local centre. Patients who are unable to tolerate the medication will be withdrawn from the study.

Compliance will be assessed six monthly. Patients will be requested to bring their remaining study medication to their six, twelve and 18 month visits for reconciliation. Unused medication will be assessed by estimating the amount of oil left in the bottle i.e. full, three quarters, half etc., and the diary card will provide supporting information if necessary.

Should any participant be hospitalised as part of a Serious Adverse Event (SAE), every effort will be made to obtain the discharge summary from the hospital concerned, and any missed doses documented.

4.6 Packaging, Labelling and Distribution of IMP

A dedicated pharmaceutical supplier and distributor will be responsible for the packing, labelling and supply of all IMPs for this study:

Nova Laboratories Ltd [name]

[contact] [contact]

Participating pharmacy departments will be responsible for dispensing the IMP and storing adequate supplies.

The study is double blind and placebo controlled, therefore neither the participant nor the investigator will be aware of the randomised IMPs. Both active and placebo IMP will have identical packaging, labelling and appearance; however, the aspirin **dose** will not be blinded due to different tablet size for 100mg and 300mg.

The bottles/containers will be labelled 'Vitamin D3 oil/placebo oil' and either 'aspirin 300mg/placebo aspirin' or 'aspirin 100mg/placebo aspirin' respectively. Bottles will be fitted with child-resistant caps and the label will state that the drug is for clinical trial use only and should be kept out of reach of children. The packaging for the active agent and placebo will be identical.

Each bottle containing Vitamin D3/placebo Vitamin D3 will hold sufficient oil for at least 6 weeks with an allowance for wastage caused by adherence of oil to the glass. The containers for the aspirin/placebo aspirin will contain sufficient tablets for six months' supply plus an additional four weeks to allow continuity of treatment should the patient's appointments be delayed. Prescriptions for a pack containing Vitamin D3/placebo and aspirin/placebo will be issued six monthly, and will show a unique code number that corresponds exactly to a numbered pack in the pharmacy.

A pre-printed, detachable label affixed to the outer carton containing the six month supply of IMP will be detached by the pharmacy member when it is dispensed. This label will then be attached to the patients' Drug Dispensing Log located in the Pharmacy Site File. Patients will be supplied with sufficient medication to last until the next visit. In the event of loss or damage to their IMP, patients will be asked to contact a member of their local research team who will arrange for them to be replaced.

IMPs will be packaged and labelled with a unique pack code according to Good Manufacturing Practice (GMP) principles, and in accordance with Annex 13 (Manufacture of Investigational Medicinal Products).

